- Subjects will also be given a Fitbit® activity tracker at this time, which will be worn on their wrist during waking hours.
- Subjects will also be given a smartphone to use for syncing the Fitbit watch (charged every 4 days as well).

Period 1: (First 8 week intervention: Either filtering/ventilation mode or sham mode): Subjects will visit the main URMC lab to have plasma CRP drawn (Blood Draw 1 of 4, perform a 6 minute walk test with their Fit Bit and wearable sensors. Study staff will then visit the subject's home, check on the indoor air quality pollution monitors, and install and turn the HEPAirX® devices "On" to start Period 1 (**Visit 1**). At this time (Visit 1) the subjects will complete the SGRQ (survey 1 of 5). **Washout Period:** After 8 weeks of either filtration or placebo operation, the subject will have another blood draw for CRP at our URMC lab (2 of 4), perform a 6 minute walk test with their Fit Bit and wearable sensors and study staff will return (**Visit**

2) to turn off the two devices for a 3 week **Washout** period. A SGRQ will also be administered at this time (Survey 2 of 5). This 3 week period was included to ensure that the Pre-filtering Period 2 health measurements are not impacted by the Period 1

filtration/ventilation. While previous studies suggest a 1 week washout is adequate for PM and other pollutant levels to return to baseline levels, we chose a 3 week washout period to ensure that the subjects' functional status will also return to baseline levels.

Period 2: (Second 8 week intervention): After the washout period, the subject will again have drawn at our URMC lab (Blood Draw 3 of 4), perform a 6 minute walk test with their Fit Bit and wearable sensors and they will complete another SGRQ (Survey 3 of 5). Study staff will then return to the subject's home (**Visit 3**) to change the HEPAirX® device to the appropriate setting depending on the subjects' Group (A or B).

After 8 weeks of operation, staff will return to the subject's home (**Visit 4**) to retrieve the HEPAirX® device, Fitbit® activity tracker, smartphone and air quality monitor. At this time, another SGRQ will be administered (Survey 4 of 5) and the subject will also submit their final blood sample for CRP (Blood Draw 4 of 4), perform a 6 minute walk test with their Fit Bit and wearable sensors. The subject will complete their final survey (Survey 5 of 5) three months after Visit 4 (week 31), concluding the study.

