4) Clinical Data Collection. The patients will receive standard of care diagnostic testing and treatment throughout the period of the study. We will collect relevant data to the evaluation and ongoing management of COPD into a secure, web-based data portal. We will maintain identifying information so that we could later add to the database as new diagnostic testing or new insights relevant to old diagnostic testing become available.

5) Subject Withdrawals: This is described to the participant in the consent form. Subjects can withdraw at any point in the trial. If the subject withdraws prior to the installation of the air quality monitor, they will be replaced by another participant.

6) Additional community resources: If agreeable, patients will be able to consent to having their name released to our partners in Community Health who will contact them to consider whether they are eligible to participate in the Rochester Healthy Homes Partnership,

6. Risks and Benefits:

Risks: This study is minimal risk, as we are simply implementing an intervention that will clean the indoor air of our subjects. The blood draws will impose a small amount of physical pain to the subject. The activity monitor is a noninvasive device worn around the wrist. The SGRQ should have minimal risk for psychological stress. For the outcome of measuring exacerbations, we will be using already existing information on these patients located in the medical record. There is a small risk of loss of confidentiality and a small risk of loss of privacy due to our accessing of your identifiable information including lab work and our entry into your home for installation of the indoor air cleaners. Please see our data storage and confidentiality plan for our methods to protect against these potential losses of confidentiality and privacy. Having an indoor air cleaner may expose the subjects to the stress of thinking of the dangers of indoor air quality

Benefits: There will be at most a transient benefit to the individual subjects.

Compensation

Payment to Subjects

Each subject will receive a total of \$580 in the form of a check to offset electricity costs to run the HEPAirX and travel for blood draws.

1. Compensation for driving to the lab (using a compensation of \$0.565 per mile with a uniform estimate of 30 miles travel for each of 4 CRP): \$80 per study subject
2. Compensation for scheduled home visits: \$25 per visit = \$100 per study subject

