E.4. Statistical Analysis. We will generate descriptive statistics for each subject, indoor air pollutant concentrations during each filtering/placebo mode session, and our main outcomes in Aim 1-Aim 3 (Aim 1: SGRQ symptom score and average daily step count; Aim 2: plasma level of CRP; Aim 3: number of healthcare encounters for AECOPD), comparing the change in each between the filtration and placebo groups. Given the crossover design, each subject will serve as their own control. Our statistical analyses are described below.

We will fit a random effects ANOVA model regressing the 8-week (Post-filtering SGRQ score (Aim 1) against the Pre-filtering SGRQ score, period ('Period 1' versus 'Period 2'), and filtering mode ('filter/ventilation mode' versus 'placebo mode'). If necessary, we will transform both post-filtering and pre-filtering SGRQ score to better satisfy model assumptions. Subjects will contribute two observations to the analysis and subjects will be included as random effects, recognizing correlations due to repeated measures on the same subject. Filtering mode will test whether the 'filtration/ventilation mode' produced a significant effect on subsequent SGRQ score than the 'placebo mode'. Next, the final survey 3 months after the 19 week intervention period concludes will be compared to survey 4 to explore the duration of observed changes. We expect that in view of the "washout period" between Period 1 and Period 2, there will be no carry-over of the effect of the intervention in Period 1 on the results for Period 2. Including period in the model allows us to assess the plausibility of this assumption. This same analysis used for Aim 1 will also be used for Aim 2, plasma CRP.

We will repeat the random effects ANOVA model, regressing the 8 week in Fitbit® measured average daily step count (Aim 1) (Post-filtering average daily step count) against the Pre-filtering average daily step count, period and filtering mode. Specifically the intervals selected for this analysis will be the week prior to Phase 1 compared to the final week of Phase 1 and the final week of the washout period compared with the final week of Phase 2. Indoor PM2.5 concentration will be analyzed similarly with the ANOVA model and will also use these same time intervals. We will repeat the random effects ANOVA model for average resting heart rate at the same time intervals.

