For Aim 3, the number of healthcare encounters for AECOPD, we will fit a Poisson regression of the number of COPD exacerbations in 8 weeks as a function of filtering mode (Filtering versus Placebo) and period. Should there be very few healthcare encounters, instead we will use a logistic regression to model whether there were any healthcare encounters. This model will allow us to evaluate the impact of filtering model on healthcare

encounters, while adjusting for period (e.g. Group A (Filtration followed by Placebo) or Group B (Placebo followed by Filtration) to determine if the order of intervention affected the outcome). Next we will compare healthcare encounters for AECOPD at the 3 month follow up period with Phase 2 outcomes in a similar way. Since this is a pilot study, power calculations are not provided, and effect estimates from the regression analyses described above will be used as preliminary data in an application for a larger, adequately powered R01 funded study.

Post hoc analyses:

1. Autonomic function: In addition to average resting heart rate, we will determine if the data are robust enough to calculate heart rate variability.
2. Genetic response: As mentioned, the stored blood may be used in a future analysis on the genetic response to air pollution related to respiratory outcomes
3. Particle Chemistry: The particles on the filters will be analyzed in the future for composition and potentially even included in cell exposure studies to determine the mechanistic impact of the pollutants.

SAFETY AND REPORTABLE EVENTS

Adverse Event Definition

An adverse event is any symptom, sign, illness, or experience, which develops or worsens during the course of the study, whether or not the event is considered related to study drug.

Serious Adverse Event

A serious adverse event is defined as any adverse medical experience that results in any of the following outcomes:

- death;
- is life-threatening;
- requires inpatient hospitalization or prolongation of existing hospitalization;
- results in persistent or significant disability/incapacity;
- is a congenital anomaly/birth defect; or
- requires medical or surgical intervention to prevent permanent impairment or damage.

Recording Adverse Events

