Appendix: Data collection form

Study Number

Sex

Age

Race

Ethnicity

Home Address

Comorbidities (OSA, sinus, DM, CHF, COPD, CRF)

Smoking

Vaccines

FEV1 Forced expiratory volume

FVC Forced vital capacity

FEV1/FVC ratio

DLCO (diffusion capacity)

TLC (total lung capacity)

Inhalers

Inhaled steroid use

Systemic steroid use

Chronic Azithromycin Use

Number of hospitalizations in past year

Home O2 use (in Liters)

CPAP/BiPAP use at night

Statin use

Symptoms (i.e. Cough, shortness of breath)

SGRQ baseline

SGRQ Period 1 end

SGRQ Period 2 start

SGRQ Period 2 end

SGRQ 3 months from the end of period 2

CRP at baseline

CRP Period 1 Week 1

CRP Period 1 end

CRP Period 2 start

CRP Period 2 week

CRP Period 2 end

Exacerbation count end of period 2

Time to exacerbation

Exacerbation count at 3 months from period 2

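### The period term in the planned crossover model cannot show whether carry-over is absent

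*Combined protocol and SAP*

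**What the plan says.** Section 5 (E.3) sets out two sequences. Group A has filtration and then placebo, Group B the reverse, with 8 weeks per period and a 3-week washout between them. On the purpose of the washout it says: "This 3 week period was included to ensure that the Pre-filtering Period 2 health measurements are not impacted by the Period 1" (the sentence goes on to name the active mode). On its length it says: "While previous studies suggest a 1 week washout is adequate for PM and other pollutant levels to return to baseline levels". Three weeks were chosen so that functional status would also recover, but no source is cited for that.

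Section 8 (E.4) models the post score on the pre score, period (1 versus 2) and mode, with a random subject effect. SGRQ and CRP share this analysis, and step count has the same terms. None of the three models contains a sequence, carry-over or mode-by-period term. After stating that no carry-over is expected, the plan says: "Including period in the model allows us to assess the plausibility of this assumption".

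For Aim 3, E.4 describes the model as "adjusting for period (e.g. Group A (Filtration followed by Placebo) or Group B (Placebo followed by Filtration) to determine if the order of intervention"; the stated aim is to see whether order made a difference. Section 6 expects little lasting effect: "There will be at most a transient benefit to the individual subjects".

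**The concern.** The period coefficient compares Period 2 with Period 1, averaged over the two sequences. A seasonal or disease-related drift moves it, and so does any filtration effect that persists into Group A's placebo period. Differential carry-over, the part that biases the treatment comparison, is aliased with sequence (equivalently, mode-by-period), and that term is not fitted.

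A quiet period term could therefore be reported as support for no carry-over, and a non-zero one as evidence of it. Neither reading follows. This matters because E.4 intends the effect estimates as preliminary data for a larger trial.

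No other planned analysis fills the gap. On PM2.5 the plan says: "Indoor PM2.5 concentration will be analyzed similarly with the ANOVA model and will also use these same time intervals". Those intervals include the final washout week, but they describe exposure, not the recovery of function or CRP. The Period 2 pre-measurement enters the models only as a covariate, and no comparison of it between Groups A and B is stated.

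**Working it through.** **Notation.** The documents give no effect size, SD or carry-over value, so there is no figure of theirs to reproduce. Let E be the true filtration effect and b the slope on the pre score. Let Lb and Lp be the filtration effect left in Group A at washout end and at Period 2 end. Let sb and sp be time shifts common to both groups at those points. Carry-over after placebo is taken as zero.

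**Cell means of post minus b × pre, apart from a constant.**
- A, Period 1: E
- A, Period 2: (sp - b·sb) + (Lp - b·Lb)
- B, Period 1: 0
- B, Period 2: E + (sp - b·sb)

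**Contrasts.**
- Mode = [(A1 - A2) + (B2 - B1)]/2 = E - (Lp - b·Lb)/2
- Period = [(A2 - A1) + (B2 - B1)]/2 = (sp - b·sb) + (Lp - b·Lb)/2
- Sequence = (A1 + A2) - (B1 + B2) = Lp - b·Lb

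**Same period coefficient, different truth** (E = -4, sb = Lb = 0, any b).
- sp = -2, Lp = 0: period = -2, mode = -4 (unbiased).
- sp = 0, Lp = -4: period = -4/2 = -2, mode = -4 + 2 = -2 (halved).
- sp = +2, Lp = -4: period = 2 - 2 = 0, mode = -2 (halved).

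Adding a sequence term would not fully settle the matter. Intercept, period, mode, sequence and carry-over make five parameters for four cell means, so carry-over stays aliased with a chance difference between the groups.

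**Size, with assumed inputs.** 10 + 10 subjects (the allocation ratio is not stated), E = -4, subject SD 15 and within-subject SD 7, giving b of about 0.79. The planned model was simulated with 6,000 trials per setting, REML, and t with 18 df for period. Brackets give the range over subject SD 10, 15, 20 by within-subject SD 5, 7, 10 (b from 0.43 to 0.93).

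| Case | Lb | Lp | sb | sp | Period by formula | Mode | Period significant |
|---|---|---|---|---|---|---|---|
| 1 | -4 | -4 | 0 | 0 | -0.4 | -3.6 [-2.9 to -3.9] | 6% [5–6%] |
| 2 | -4 | -2 | 0 | 0 | 0.6 | -4.6 [-3.9 to -4.9] | 6% [5–7%] |
| 3 | -4 | 0 | 0 | 0 | 1.6 | -5.6 [-4.8 to -5.9] | 9% [6–14%] |
| 4 | 0 | -4 | 0 | 2 | 0 | -2.0 [-1.9 to -2.0] | 6% [5–6%] |
| 5 | 0 | 0 | 0 | 4 | 4 | unbiased | 28% [17–50%] |
| 6 | 0 | 0 | 4 | 4 | 0.8 | unbiased | 7% [5–11%] |

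As a check by formula, case 3 gives mode = -4 - (0 + 0.79 × 4)/2 = -5.6. With no carry-over and no shift, mode is -3.98 and period is significant in 5.6%. Formula and simulation agree within 0.1 for mode in every setting.

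The direction of bias in case 2 depends on b. Mode is about -3 - 2b, so the effect is exaggerated only if b > 0.5. At SDs 10/10 (b = 0.43) it is -3.9.

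Halving the carry-over (and the shift in case 4) gives mode -3.8, -4.3, -4.8 and -3.0 in cases 1 to 4, with period significant in about 6% each time.

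**Precision of a direct look at washout end.** The SD of a change score is √2 × within-subject SD, because the subject SD cancels. The 95% half-width is t(18) × √2 × SD × √(2/10) = 2.101 × 9.90 × 0.447 = 9.3 at SD 7, and 6.6 and 13.3 at SD 5 and 10. Power for a 4-point difference is 14%, 22% and 9% respectively.

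**The case against.** The algebra is hard to contest, so the case against turns on scope and remedy.

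- **The period term is not empty.** It contains (Lp - b·Lb)/2, the same quantity that biases mode, and would be informative if time shifts were known to be small. That is true, but it needs an outside assumption the plan does not make, which is what confounding means here.
- **Nothing planned changes.** There is no decision rule on period, and the mode estimate is the same however period is read. This stands and keeps the point minor.
- **The mode biases are not caused by the sentence.** They would be the same if it were deleted, and cases 1 to 4 assume full persistence at one or both points, which is extreme. This also stands. The biases show only what a quiet period term can fail to reveal.
- **The suggested contrast has its own blind spot.** It estimates Lb alone, whereas the bias depends on Lp - b·Lb. Simulated at SDs 15/7, a test on it was significant in 14% of trials in case 1 (bias about 0.4) and in 5%, the null rate, in case 4 (bias about 2.0). Carry-over visible at washout end may also be largely absorbed by the covariate. It should therefore be reported as an estimate with its limits stated and never used as a gate.
- **A persistence analysis is already planned.** The 3-month survey is compared with Survey 4. It covers SGRQ only, is not stated by group, and looks at 3 months rather than 3 weeks, so it does not support the sentence.

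**Conclusion.** The concern holds, as a minor point of interpretation. The planned models do not have the property that E.4 claims for them: period mixes a time shift with carry-over and cannot by itself support or refute the no-carry-over assumption. That result is algebraic and does not depend on the assumed SDs.

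The sizes do rest on assumptions. At the central inputs, the bias in mode in cases 1 to 4 is about 0.15, 0.2, 0.55 and 0.7 of the mode estimate's sampling SD (2.9; range 2.0 to 3.9).

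This does not establish that carry-over exists. The Aim 3 wording is a separate, smaller ambiguity: it explains period by naming the two sequences, so a reader cannot tell which variable will be fitted. The carry-over sentence precedes the step-count paragraph, so applying it to steps is inference from the shared model terms.

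**What to change.** In section 8 (E.4), delete the sentence about assessing the assumption. Keep period in the model and state: *Period adjusts for time. No carry-over is an assumption that this trial cannot confirm.*

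Report the Group A minus Group B difference in change from first baseline to washout end, as an estimate with a 95% CI and not as a pre-test:
- SGRQ: Survey 3 minus Survey 1.
- CRP: Blood Draw 3 minus Blood Draw 1.
- Steps: final washout week minus the week before Phase 1.

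Say beside it that the estimate is imprecise and misses carry-over not visible at washout end.

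For Aim 3, state whether the variable is period (1 versus 2) or sequence (Group A versus B). Keep period in the model and base any statement about order on sequence, noting that sequence also carries chance differences between the groups.

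The cost is two wording changes and one between-group estimate for each of three outcomes. No new data are needed. The appendix form already has baseline fields and the entries "SGRQ Period 2 start" and "CRP Period 2 start", and E.4 already defines the step intervals. The estimate does not cover Aim 3, which has no pre-measurement.

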E.1. Study Population. We will recruit a total of 20 adult (≥ 18 years of age) men and women with severe COPD ($FEV1 < 50\%$), who live in Rochester, NY, have completed pulmonary rehabilitation, and have suffered from an AECOPD in the past year. **E.2. Health Outcomes.** Our primary endpoints will be the symptom score from the St. George's Respiratory Questionnaire (SGRQ; marker of functional status) described above in Section B.3 and the average daily count of steps taken using a Fitbit® brand wearable sensor (Aim 1). Our secondary endpoints are Plasma CRP measurements (Aim 2) and healthcare contacts for AECOPD (Aim 3). The subjects will wear the Fitbit® watch around their wrist during waking hours, which will automatically collect the daily count of steps and report this electronically to the research team via a secure account (Described below). The subjects will travel to the URMC lab at the specified time (described below) to have their plasma CRP drawn.

E.3. Study Protocol. We will conduct a randomized, blinded, crossover trial, where each of the 20 total subjects will be randomly assigned to **Group A** (Period 1 = 8 weeks of filtration/ventilation mode, 3 week washout period, Period 2 = 8 weeks of placebo mode [device runs but no filtration/ventilation]) or **Group B** (Period 1 = 8 weeks of placebo mode, 3 week washout period, Period 2 = 8 weeks of filtration/ventilation mode). Subjects will be blinded to which group they are randomly assigned, and only staff installing and monitoring the HEPAirX device and air pollution monitoring equipment, and not staff collecting or analyzing health outcomes, will know the assigned group. In the placebo mode of operation, the HEPAirX unit operates in exactly the same way (i.e. will look and sound the same), but it does not filter air to remove particles or have outdoor air exchanges to reduce gaseous pollutants. With 20 HEPAirX machines available and 2 required per subject, the timing of enrollment will be split into 2 groups of 10 patients (Two 19 week periods).

After getting informed consent from each study participant, we will schedule the 1st home visit within 2 weeks. Once consent to participate in the study has been obtained, we will provide subjects with:

- Five simple indoor air quality monitors which the subject will plug into an electrical outlet and set on a tabletop in a low traffic area of their living room and bedroom.

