rate which will also be a proxy for activity. Participants will be dispensed a wristband (and charger) to wear at home for the entire study period. This Fitbit® will be synced to our secure tablet computer at the home visit intervals and we will access the data on the secure web-based portal. We will manage the accounts for each Fitbit®, but the subjects will have temporary access to the accounts. Subjects will be provided with a smartphone which will have only Wi-Fi capabilities and the Fitbit app installed. Subjects will sync their Fitbit with this device on a weekly basis. In this case, the wristband uploads the data to the app through blue tooth technology and ultimately onto a secure HIPAA compliant cloud. Subjects will be given the charging cord and instructed to charge the Fitbit® device every 7 days. When the study is complete, the FitBit® and smartphone will be collected at the final home visit. If the patient is not able to coordinate this data collection, we will help them sync their watch during home visits and will be available to help as needed through the study.

3) Home air quality monitoring

The simple corded air quality monitors (for particles and CO₂, provided once consent has been obtained, will be placed in the subjects' home and will take continuous measurements over the course of the study. This will be checked at the midpoint of the study and collected at the conclusion of the study. The monitors, will be sent to AirViz so they can extract the anonymized raw data from the air quality monitors and review the information captured to ensure data quality. Once QA review is complete, the data will be forwarded to us for our research analysis at the end of the study. AirViz Inc. will not receive any information that identifies the subjects, nor will they take part in analyzing or interpreting the results of the air quality data. Furthermore, after removal from subject homes, the filters from the HEPAirX® devices will be retained (not discarded) and will be used in a future analysis with links retained to subject ID and current study outcomes.

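### Step count, PM2.5 and resting heart rate are modelled from the last 7 of 56 days of each period; a longer pre-specified window would be more robust and probably more precise

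*Combined protocol and SAP*

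**What the plan says.** E.2 (Health Outcomes) names average daily step count as a primary endpoint, next to the SGRQ symptom score. E.3 (Study Protocol) gives each mode 8 weeks, for example "Period 1 = 8 weeks of filtration/ventilation mode, 3 week washout period" in Group A.

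E.4 (Statistical Analysis) defines the first pair of windows for the step-count model as "the week prior to Phase 1 compared to the final week of Phase 1". In the second period the pre-value comes from the last of the three washout weeks and the post-value from week 8 on treatment. "Phase" here is the "Period" of E.3. For the pollutant, "Indoor PM2.5 concentration will be analyzed similarly with the ANOVA model and will also use these same time intervals". The model is then repeated for average resting heart rate at the same intervals. E.4 gives no reason for a one-week window.

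The recording is much longer than the window. Under Protocol (Methods and Procedures), item 2 has the wristband dispensed for the whole study and counting steps continuously, and item 3 says that the air monitors "will take continuous measurements over the course of the study". Heart rate comes from the same wristband. That it too is recorded throughout is an inference, and E.2 limits wear to waking hours.

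The sections on wear and analysis contain no definition of a valid day, no minimum wear rule and no sensitivity analysis with a longer window.

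**The concern.** The post-value that enters the model is a mean over 7 of 56 on-treatment days (7/56 = 12.5%). With 20 patients and two observations each, a chest infection, bad weather, travel or poor wear in that week sets a patient's result for the whole period, even where earlier weeks were recorded well. These patients have severe COPD and an exacerbation in the past year, and the E.3 diary anticipates respiratory symptoms, so an unrepresentative week is not a remote possibility.

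At stake is the precision of the filter effect on a primary endpoint, and of the PM2.5 contrast that shows whether the device changed exposure. E.4 says the effect estimates will serve as preliminary data for a larger trial, so avoidable noise carries into its planning.

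**Working it through.** **No plan figure to reproduce.** E.4 gives no power calculation, standard deviation or precision target. The timeline is consistent: 8 + 3 + 8 = 19 weeks, as E.3 states.

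**Inputs from the documents.** 20 patients; two 8-week periods; a post-value of 1 week; recording throughout.

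**Assumptions, not in the documents.** Weekly means have lag-1 correlation ρ from 0 to 0.5. Week-level noise is a share s = 0.25 to 0.75 of the within-patient variance of a one-week post-value; the rest is patient-by-period variation that more weeks cannot reduce. The pre-period week is left unchanged and its role as covariate is not modelled.

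**Step 1: variance of an m-week mean relative to one week.**
R = [1 + 2 Σ (1 − k/m) ρ^k] / m, with k from 1 to m − 1.

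| ρ | m = 4 (weeks 5–8) | m = 7 (weeks 2–8) |
|---|---|---|
| 0 | 0.25 | 0.14 |
| 0.3 | 0.39 | 0.24 |
| 0.5 | 0.52 | 0.35 |

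**Step 2: standard-error ratio, longer window to final week.** Ratio = √(1 − s + sR).

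- Weeks 5–8, least favourable (s = 0.25, R = 0.516): √0.879 = 0.94, a 6% reduction.
- Weeks 5–8, most favourable (s = 0.75, R = 0.25): √0.4375 = 0.66, a 34% reduction.
- Weeks 2–8, same two corners: √0.837 = 0.91 and √0.357 = 0.60, reductions of 9% and 40%.

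The lower limit depends on the assumed floor for s. At s = 0.125 the weeks 5–8 reduction is only 3% to 5% (√0.939 = 0.97; √0.906 = 0.95).

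**Step 3: dilution if the effect builds linearly**, using mid-week values, weeks 5–8 against week 8.

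- Full by week 4: 1.00 / 1.00, no dilution.
- Full at week 6: (0.75 + 0.917 + 1 + 1)/4 = 0.917 against 1.00, 8% dilution.
- Full at week 8: (4.5 + 5.5 + 6.5 + 7.5)/(4 × 8) = 0.75 against 7.5/8 = 0.9375, ratio 0.80, 20% dilution.

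**Step 4: net signal-to-noise**, retained effect divided by standard-error ratio.

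| Onset | s = 0.25, ρ = 0.5 | s = 0.75, ρ = 0 |
|---|---|---|
| Full by week 4 | 1/0.9375 = 1.07 | 1/0.661 = 1.51 |
| Full at week 6 | 0.917/0.9375 = 0.98 | 0.917/0.661 = 1.39 |
| Full at week 8 | 0.80/0.9375 = 0.85 | 0.80/0.661 = 1.21 |

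**Cross-check with a daily model.** Variance of a period mean = τ² + σ²f(m), with autocorrelated days, τ²/σ² from 0 to 1 and daily correlation 0 to 0.8 (all assumed). The last 28 days give a standard error 0.50 to 0.95 times that of the last 7. At τ²/σ² = 0.25 and correlation 0.3, net signal-to-noise for 28 days against 7 is 1.25 if the effect is full by day 28 and 1.00 if it builds to day 56. The full 56-day mean does worse under slow onset: 0.99 and 0.70 in the same two cases. That is why the whole period is not proposed for steps.

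**The case against.** The strongest defence is that the final week is a proper end-of-treatment estimand. SGRQ and CRP are read at 8 weeks, and a final-week step count lines up with them, with matched 7-day pre and post windows. A weeks 5 to 8 mean answers a slightly different question. This stands, and it is why the final-week result should still be reported.

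A reader might infer that the one-week window contradicts the plan's own timing, because the effect should have levelled off by week 5. The documents do not support that. E.3 says "previous studies suggest a 1 week washout is adequate for PM and other pollutant levels to return to baseline levels" and chooses 3 weeks so that functional status also returns to baseline. Both describe decay after switch-off, and the 3 weeks is a design choice, not a measured time. Nothing states how fast steps improve after switch-on. Carrying the 1-week figure over to onset is reasonable for a pollutant in a room; for steps it is a guess.

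A reader might also infer that an unsynced final week is lost. Item 2 of the methods has the wristband synced at home visits with staff help, and Section 7 has data downloaded at least at the end of each period. Non-wear and illness remain the risks, not syncing.

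Nor is the remaining PM2.5 record wholly unused: E.4 plans descriptive statistics of pollutant concentrations during each mode session. PM2.5 is also neither a primary nor a secondary endpoint in E.2.

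Finally, this is a pilot with no precision target, and the raw data would allow a longer-window analysis later. True, but a window chosen after unblinding would look data-driven.

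**Conclusion.** The point holds as one of efficiency and robustness. Nothing here shows bias or an invalid test.

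For PM2.5 the case is clear: a weeks 2 to 8 mean uses data already collected and follows the plan's own pollutant figure, so the dilution risk is small if onset is about as fast as offset. Under the assumed noise shares the standard error falls by about 9% to 40%.

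For steps and resting heart rate a weeks 5 to 8 mean is protection against one bad week and a likely, not certain, gain in precision. The variance reduction alone would be worth 20/0.879 ≈ 23 to 20/0.4375 ≈ 46 patients analysed as planned, but that range should not be read as the net gain, because it assumes no dilution. With onset allowed for, the outcome runs from a 15% loss to a 51% gain in signal-to-noise. The noise shares, autocorrelation and onset shapes are all assumptions, and the benefit shrinks if week-level noise is below 25% of the variance.

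**What to change.** In E.4, before unblinding:

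- **PM2.5:** replace the final-week post-value with the mean of weeks 2 to 8 of each period.
- **Steps and resting heart rate:** define the post-value as the mean of valid days in weeks 5 to 8 of each period. State what counts as a valid day and how many are needed, since the plan now gives neither.
- **All three:** keep the stated pre-period weeks as the covariate.
- **Sensitivity analysis:** report the final-week result for steps and resting heart rate alongside, as the end-of-treatment estimate. If the two differ materially, slow onset is one explanation to consider.

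The cost is SAP wording; no new visits, devices or data are needed. The downside is some dilution of the step and heart-rate effects if benefit is still building after week 4 (8% if full at week 6, 20% if linear to week 8).
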